Appendix 6: Schedule of Assessments

	Screening ^a	Randomizati on ^b	Treatment period										Follow-up			
			-4	Day -1	0 ^c	1	2	3	4	8	9	10	11	12 ^d	14	16
Week	-4	Day -1	0 ^c	1	2	3	4	8	9	10	11	12 ^d	14	16	18	
Day (range)		-1	1	8	15±1	22±1	29±1	57±1	64±1	71±2	78±2	85±3	99±3	113±3	127±3	
Visit	1	2	2	3	4	5	6	7	8	9	10	11	12	13	14	
Informed consent	×															
Inclusion/exclusion criteria	×															
Demographic data	×	×														
Medical history	×	×														
Concomitant medication	×	×	×	×	×	×	×	×	×	×	×	×	×	×	×	×
Vital signs	×	×						×	×				×			
Height	×															
Body weight	×	×						×	×				×			
Physical examination	×	×						×	×				×			
Serology tests ^e	×															
Hematology, clinical chemistry, and coagulation	×	×						×	×				×			
Urinalysis	×	×						×	×				×			

	Screening ^a	Randomizati on ^b	Treatment period										Follow-up				
			Week	-4	Day -1	0 ^c	1	2	3	4	8	9	10	11	12 ^d	14	16
Day (range)		-1			1	8	15±1	22±1	29±1	57±1	64±1	71±2	78±2	85±3	99±3	113±3	127±3
Visit	1	2	2	3	4	5	6	7	8	9	10	11	12	13	14		
Pregnancy test ^f	×	×					×	×					×				
FSH ^g	×																
Pulmonary function	×												×				
Injection of GMA301 or placebo				×					×	×							
Pharmacokinetics sampling				×	×	×	×	×	×	×	×	×	×	×	×	×	×
Immunogenicity (ADA) ^h				×		×			×	×				×			×
NT-proBNP			×						×	×				×			
AE recording	×	×	×	×	×	×	×	×	×	×	×	×	×	×	×	×	×
12-lead ECG	×	×							×	×				×			
RHC	×													×			
Echocardiogram	×									×				×			
6MWT (Borg dyspnea scale)	×													×			
WHO function classification	×	×								×				×			

	Screening ^a	Randomization ^b	Treatment period										Follow-up				
			Week	-4	Day -1	0 ^c	1	2	3	4	8	9	10	11	12 ^d	14	16
Day (range)		-1			1	8	15±1	22±1	29±1	57±1	64±1	71±2	78±2	85±3	99±3	113±3	127±3
Visit		2		1	3	4	5	6	7	8	9	10	11	12	13	14	
REVEAL risk score		×												×			

Abbreviations: 6MWT = six-minute walk test; ADA = Anti-drug antibodies; ECG = electrocardiogram; FSH= follicle stimulating hormone; RHC = right heart catheterization.

- a. Screening period will be up to 4 weeks. If a Screening test was performed within 3 days prior to Week 0, the results can be used as baseline (Week 0) results. No need to repeat the test at Week 0.
- b. Day -1 the randomization day can also be the first day of Week 0, ie, the baseline blood sampling and information collection can be conducted just before the first dosing.
- c. The samples at Week 0 will be collected on Day 1 of Week 0 before the first dosing.
- d. Tests can also be done on the last day of Week 11. If a subject discontinues the visit in advance, it would be better to ask the subject to complete the Week 12 examinations.
- e. Serology tests refer to Hepatitis B surface antigen, Hepatitis C antibody, and Human Immunodeficiency Virus antibodies ([Appendix 2](#)).
- f. Women of childbearing potential will perform pregnancy test in serum at Screening and in urine at randomization and Weeks 4, 8, and 12.
- g. FSH test will be performed at the same time with serum pregnancy test at Screening.
- h. ADA will be collected at: Week 0 (pre-dose of the 1st dose), Week 2, Week 4 (prior to 2nd dose), Week 8 (prior to 3rd dose), Week 12 and Week 18 (end of follow-up).

Pharmacokinetics sampling:

Pharmacokinetics serum samples will be obtained for PK assessments at the following timepoints (\pm Time window):

[figure not shown]
Dose 1st: predose, 4 (\pm 15 min), 8 (\pm 30 min), 24 (\pm 120 min), 72 (\pm 240 min), 168 (Day 8; \pm 480 min), 336 (Day 15; \pm 1 day), 504 (Day 22; \pm 1 day), and 672 (Day 29; \pm 1 day) hours post dose.

Dose 3rd: predose, 4 (\pm 15 min), 8 (\pm 30 min), 24 (\pm 120 min), 72 (\pm 240 min), 168 (Day 8; \pm 480 min), 336 (Day 15; \pm 1 Day), 504 (Day 22; \pm 1 day), 672 (Day 29; \pm 1 day), 1008 (Day 43; \pm 2 day), 1344 (Day 57; \pm 3 day), 1680 (Day 71; \pm 3 day) hours postdose.

The samples of the 672h post 1st dose will be collected before the 2nd dose.

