3.5. Safety Review Committee (SRC)

A SRC will be established to assess safety profile for each cohort to determine dose escalation. The SRC will be composed of 3 investigators, the Covance Lead Project Physician, the Gmax Lead Project Physician, and another unblinded physician who is not involved in this study.

SRC Operation. The SRC will meet after 8 of 12 subjects have received 3 doses of the study drug with a 28-day follow-up and the entire cohort of 12 subjects has been randomized.

The initial SRC meeting will review safety data from the initial 8 subjects in Cohort 1 who have completed 3 doses of the study drug and have been followed for 28 days following the third dose. Upon SRC's approval, Cohort 2 will be opened for recruitment once the residual 4 subjects have been randomized in Cohort 1. The second meeting of the SRC will review safety data from the initial 8 subjects in Cohort 2 **and the 4 residual subjects from Cohort 1 who were not yet reviewed.** Upon SRC's approval, once the residual 4 subjects in Cohort 2 are randomized, Cohort 3 can be initiated for recruitment. If fewer than 8 subjects (including 8) in a cohort have completed administration and follow-up regimen, with some drop-outs, their safety data will be reviewed by SRC aiming to determine whether the next cohort with a higher dose can be started. Additionally, ad hoc meetings will be organized in case of any SAE or adverse event with maximum severity that could be drug-related.

SRC reviews will include, but not limited to, clinical findings, vital signs, hematology and biochemistry results, ECG, AEs, and SAEs. The composition, operation, and management of the SRC will be described in detail in the SRC charter.

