- Any clinically relevant sign or symptom (eg, Class IV heart failure) that, in the opinion of the Investigator (or designee), warrants subject withdrawal.

Subject who didn't get IMP treatment within protocol defined timeline with any reason can get back to the IMP treatment with investigator or SRC's evaluation and agreement.

All the discontinuation must be documented accordingly. If a subject is withdrawn, the Sponsor will be notified in 24 hours and the date and reason(s) for the withdrawal will be documented in electronic Case Report Form (eCRF). In this case, efforts in any ways must be made to complete the follow up assessments. ([Appendix 6](#)). Other medical procedures may be performed at the Investigator's discretion. The Investigator may also request subjects to return for additional Follow-up visits. All AEs will be followed until recovery or stabilization.

Cohort discontinuation and study termination

The SRC will discontinue or stop the cohort or even the study in case of :

- Two cases discontinuations in a cohort due to events related to the study drug under the diagnosis of the investigators;
- Single case with severe allergic event related to study drug;
- Known and expected AEs are with increased frequency, severity and or long lasting.

The sponsor can terminate the study with notification to the investigators.

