8. SAMPLE SIZE AND DATA ANALYSIS

8.1. General Analysis

Statistical analyses will be descriptive only, with no hypothesis testing. Analyses will be performed in SAS®. Summary tables will present results for each of the three GMA301 doses. Descriptive statistics including the number (n), the arithmetic mean (Mean), standard deviation (SD), median, the minimum value (Min), and the maximum value (Max) will be presented for continuous variables, and the number of subjects (n) and the percentage (%) will be presented for categorical and ordinal variables. All study data will also be presented in by subject data listings. The details of the statistical analysis will be described in the Statistical Analysis Plan (SAP).

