8.2. Determination of Sample Size

No formal statistical assessment, in terms of sample size, has been conducted. Approximately 36 subjects will be randomized into 3 treatment cohorts with GMA301-assigned subjects receiving either 300, 600, or 1000 mg injections of the study drug depending on their assigned cohort. Each cohort will include 12 subjects, 9 of whom will be administered active GMA301 and 3 of whom will receive placebo.

The number of subjects in each cohort of the present study is common in early clinical pharmacology studies and is considered sufficient to achieve the objectives of the study.

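### After dose 3 the visit table counts from Day 1, while PK sampling and the SRC follow-up count from the dose, and nothing links the two clocks

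*Combined protocol and SAP*

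**What the plan says.** **Visit table (Appendix 6).** Dose 3 is at Day 57±1. Weeks 9, 10, 11, 12, 14, 16 and 18 are at Days 64±1, 71±2, 78±2, 85±3, 99±3, 113±3 and 127±3, all counted from Day 1. Footnote d adds for Week 12: "Tests can also be done on the last day of Week 11".

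**PK list (Appendix 6).** The same visits are timed in hours after the third dose, with separate windows: 168 h ±8 h; 336, 504 and 672 h ±1 day; 1008 h ±2 days; 1344 and 1680 h ±3 days. The Week 12 and Week 14 entries read "672 (Day 29; \pm 1 day), 1008 (Day 43; \pm 2 day".

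**SRC (Section 3.5).** The first escalation review covers the initial subjects who "have completed 3 doses of the study drug and have been followed for 28 days following the third dose". The data reviewed include vital signs, hematology, biochemistry, ECG and adverse events.

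**Late dosing (Section 3.6).** "Subject who didn't get IMP treatment within protocol defined timeline with any reason can get back to the IMP treatment", subject to agreement by the investigator or the SRC. No maximum delay is stated, and nothing says how later visits move.

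**What hangs on Week 12 (Appendix 6).** It is the only scheduled laboratory, ECG and vital-sign assessment after the dose 3 visit, and the only post-baseline right heart catheterization (RHC) and six-minute walk test. Adverse event recording and PK sampling continue to Week 18.

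**The concern.** One visit is governed by two reference points that move independently. A site working from the visit table can keep every visit in window and still take PK samples outside the PK window. At Week 12 it can also collect the last scheduled safety laboratory tests, ECG and vital signs before the 28 days named in Section 3.5.

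When dose 3 is late, the protocol does not say whether Week 12 stays at Day 85 or follows the dose. If it stays, the hemodynamic and trough measurements labelled Week 12 are taken at a different point of the dosing interval from those of other subjects. Trough concentration, accumulation ratio and exposure-response are planned outputs, with nine active subjects per dose.

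**Working it through.** **Inputs.** Visit days, windows and PK times: Appendix 6. The 28 days: Section 3.5. Half-life averages of 503.75 to 565.63 h (21.0 to 23.6 days) and mono-exponential decline in most healthy subjects: Section 1.5.2. The length of any dosing delay is assumed.

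**1. Nominal days agree.** Study day = 57 + hours/24. The hours 168, 336, 504, 672, 1008, 1344 and 1680 give Days 64, 71, 78, 85, 99, 113 and 127, exactly the table's days. The conflict lies in the windows and the anchor.

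**2. Days since dose 3, dose 3 on Days 56-58.** Earliest = earliest visit day - 58; latest = latest visit day - 56.

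| Visit | Table allows (days) | PK window (days) | Whole-day pairs inside PK window |
|---|---|---|---|
| Week 9 | 5-9 | 6.7-7.3 | 3 of 9 |
| Week 10 | 11-17 | 13-15 | 9 of 15 |
| Week 11 | 18-24 | 20-22 | 9 of 15 |
| Week 12 | 24-32 | 27-29 | 9 of 21 |
| Week 14 | 38-46 | 40-44 | 15 of 21 |
| Week 16 | 52-60 | 53-59 | 19 of 21 |
| Week 18 | 66-74 | 67-73 | 19 of 21 |

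The table window itself is wider than the PK window at Weeks 9, 10, 11, 12 and 14. At Weeks 16 and 18 the widths are equal, and a miss needs an off-day dose plus a visit at the edge of its window.

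**3. Week 12 in detail (visit Days 82-88).**

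| Dose 3 | Days since dose | Days inside both windows | Visit days short of 28 | Day 84 falls at |
|---|---|---|---|---|
| Day 56 | 26-32 | 83-85 | 2 of 7 | 28 days |
| Day 57 | 25-31 | 84-86 | 3 of 7 | 27 days |
| Day 58 | 24-30 | 85-87 | 4 of 7 | 26 days |

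Outside the PK window: 21 - 9 = 12 of 21 pairs. Short of 28 days: 2 + 3 + 4 = 9 of 21.

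**4. Late dose 3 on Day d.** The PK window opens at d + 27 and the table window closes at Day 88. They stop overlapping when d + 27 > 88, that is from Day 62.

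**5. Concentration at Week 12.** Relative level = sum over the three doses of 2^(-hours since dose / half-life). Doses 1 and 2 are taken on Days 1 and 29. The planned level, with dose 3 on Day 57 and the visit on Day 85, is

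- 503.75 h: 0.397 + 0.157 + 0.062 = 0.616
- 565.63 h: 0.439 + 0.193 + 0.085 = 0.716 (unrounded sum)

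| Case | Days since dose 3 | Relative to plan |
|---|---|---|
| Dose Day 58, visit Day 82 | 24 | 1.11-1.13 |
| Dose Day 57, visit Day 84 | 27 | 1.03 |
| Dose Day 56, visit Day 88 | 32 | 0.89-0.90 |
| Dose 7 days late, visit Day 85 | 21 | 1.14-1.17 |
| Dose 14 days late, visit Day 85 | 14 | 1.31-1.38 |
| Dose 14 days late, visit moved to Day 99 | 28 | 0.87 |

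For the 14-day case at 503.75 h: (0.630 + 0.157 + 0.062)/0.616 = 1.38. One such subject among nine moves the cohort mean concentration by 31.2/9 to 37.8/9, about 3.5% to 4.2%.

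**The case against.** The strongest reply is that the nominal days agree exactly and that, with dose 3 on time, three Week 12 days always satisfy both windows, so a site that applies both complies. Section 7.1.1 also requires changes to PK times to be agreed with the sponsor and documented. This stands for on-time dosing: the fault is that many permitted days miss the PK window, not that compliance is impossible. It does not answer the late dose, for which no common day need exist.

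Four stronger readings are tempting and are not supported:

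- **Footnote d is the cause.** Day 84 already lies inside 85±3. It is within the PK window for dose 3 on Day 56 or 57 and misses it only for Day 58. Deleting the footnote alone would change nothing.
- **The SRC criterion cannot be met.** Section 3.5 asks for elapsed follow-up and does not tie it to the Week 12 visit. Adverse event recording to Week 18 can supply it, Sections 7.2.2 to 7.2.4 allow extra laboratory tests, vital signs and ECGs, and operating detail is left to a charter. What remains is that the scheduled objective data can stop at day 24-27.
- **A 14-day delay gives 1.5 to 1.6 times the intended exposure.** That counts dose 3 alone. With half-lives of 21 days or more, doses 1 and 2 still contribute, and the ratio is 1.31 to 1.38.
- **A late-dosed subject necessarily has the RHC at Day 85.** The protocol is silent; Day 85 is what the table gives if nothing is moved.

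Nor do the documents relate trough concentration to hemodynamics or walking distance, so a shift in those endpoints cannot be sized.

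**Conclusion.** The point holds as a conflict between stated rules. Appendix 6 runs two clocks after dose 3 and Section 3.5 follows the second. At Week 12, 12 of 21 permitted day pairs miss the PK window and 9 of 21 fall short of 28 days. Section 3.6 opens the way to a dose date from which no visit day meets both windows.

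The size is moderate. Modelled Week 12 concentration stays within -11% to +13% of plan inside the permitted windows; a delay of a week or more makes the shift larger. These figures rest on healthy-subject half-lives, mono-exponential decline, on-schedule doses 1 and 2 and an assumed delay.

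Section 8.1 states "Statistical analyses will be descriptive only, with no hypothesis testing", so no error rate is affected. The consequences fall on PK deviations, on exposure-response and trough summaries, on how the Week 12 results are read, and on how far the SRC's scheduled objective safety data extend.

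**What to change.** Reconcile Sections 3.5 and 3.6 with Appendix 6:

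- Express Weeks 9, 10, 11, 12, 14, 16 and 18 as 7, 14, 21, 28, 42, 56 and 70 days after the actual third dose. Use the PK windows already in Appendix 6 (±8 hours; ±1, ±1, ±1, ±2, ±3, ±3 days).
- State that the same anchor applies when dose 3 is late. This concerns assessment timing only; whether a late dose is given stays with Section 3.6.
- Reconcile the Week 12 window and footnote d with the 28-day follow-up, so that the scheduled safety data cover the period Section 3.5 states. The PK window alone does not do this, because it still admits day 27.
- Record actual days since dose 3 and use them in the PK and exposure-response summaries.

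The cost is an edit to Appendix 6 with matching wording in Sections 3.5 and 3.6, and less freedom in booking Week 12: three days instead of seven for a given dose date. On-schedule concentration would then vary by about ±3%. Re-anchoring does not fully restore the plan: after a 14-day delay the level is still about 13% below it, because doses 1 and 2 have decayed further.

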1.5.2. Pharmacokinetics

Pharmacokinetic results were obtained from the same study that was performed in Australia. All individuals in the study exhibited quantifiable plasma GMA301 concentrations at the first timepoint of 4 hours. Most individuals appeared to exhibit mono-exponential pharmacokinetics, with a slow decline in plasma concentrations after attainment of Maximum Observed Serum Concentration (C_{max}). Terminal half-life was long with average values ranging from 503.75 hours to 565.63 hours.

Other pharmacokinetic values of GMA301 refer to clinical study report of GMA301 Australia study.¹⁹

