2.2.2. Secondary Endpoints

- Pharmacokinetics
 - Area under the serum concentration- time curve from time zero to the last measurable concentration (AUC_{0-t})
 - Area under the serum concentration- time curve over a dosing interval (AUC_{0- τ})
 - Observed maximum serum concentration (C_{max})
 - Area under the serum concentration-time curve from time zero to infinity (AUC_{0-inf})
 - Time to maximum serum concentration (T_{max})
 - Terminal elimination half-life (t_{1/2})
 - Volume of distribution
 - Trough concentration
 - Clearance
 - Accumulation ratio
- Comparison of GMA301 treatment effect at Week 12 versus baseline regarding the hemodynamic parameters based on RHC. Parameters include but are not limited to:
 - Pulmonary vascular resistance (PVR)
 - Mean pulmonary arterial pressure (mPAP)
 - Cardiac index
- Comparing the following treatment effect metrics:
 - 6MWT distance (Week 12 versus Screening)
 - NT-pro BNP level (Weeks 4, 8, and 12 versus baseline)
 - WHO functional class (Weeks 8 and 12 versus baseline)

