5.2. Study drug Administration

The 300, 600, and 1000 mg doses of GMA301 and matching placebo will be administered Q4W via IV injection by slow push for 12 weeks.

The study drug will be injected at an approximate rate of no more than 4 mL/min. The syringes should be connected to the previously inserted cannula for administration.

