7.1. Pharmacokinetic Assessments

7.1.1. Sample Collection and Processing

Blood samples will be collected by venipuncture or cannulation at the times indicated in the Schedule of Assessments in [Appendix 6](#).

Up to 3 additional blood samples may be taken from each subject per treatment period, with the maximum volume of blood withdrawn per subject not exceeding the limit detailed in [Appendix 3](#). Any changes to the scheduled times of PK assessments will be agreed with the Sponsor and documented in the TMF.

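### The first post-dose PK sample comes 4 h after an IV push, so Tmax is uninformative and Cmax may understate the peak by an amount the documents do not fix

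*Combined protocol and SAP*

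**What the plan says.** Section 5.2 has the drug "administered Q4W via IV injection by slow push for 12 weeks", and adds: "The study drug will be injected at an approximate rate of no more than 4 mL/min". The injected volume is not given.

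The sampling list in Appendix 6 begins "Dose 1st: predose, 4" h for the first dose and "Dose 3rd: predose, 4" h for the third. Each 4 h sample has a window of 15 minutes either way. The next times are 8, 24 and 72 h. Appendix 6 does not say whether time zero is the start or the end of the injection.

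Section 2.2.2 lists Cmax, as an observed maximum, and "Time to maximum serum concentration" among the secondary PK endpoints. Section 8.5 specifies non-compartmental analysis, so both are read directly from the samples.

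On profile shape, section 1.5.2 reports of the healthy-volunteer study: "Most individuals appeared to exhibit mono-exponential pharmacokinetics", with a slow decline and mean terminal half-lives of 503.75 to 565.63 h. That study's first sample was also at 4 h. Table 1 (section 1.4) gives monkey Cmax, half-life and AUC, but no sampling times.

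Section 7.1.1 leaves some room: "Up to 3 additional blood samples may be taken from each subject per treatment period", within the blood-volume limit of Appendix 3. It fixes no early time for them.

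**The concern.** After an IV push the highest serum concentration is expected at about the end of injection. At the maximum rate of 4 mL/min, an assumed volume of 10 to 100 mL would take 2.5 to 25 minutes. The grid is blind from then until 4 h.

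Two listed endpoints are touched. Tmax cannot take the value it is meant to measure. Cmax is the highest concentration at 4 h or later, which may or may not be close to the peak. Exposure-response is a secondary objective (section 2.1.2), and section 1.6 says the PK data will help set doses and regimen for later studies. A Cmax of unknown relation to the peak would be carried into that work. The earlier human study has the same gap, so this trial as planned would leave the question open again.

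**Working it through.** **The plan's own count.** Dose 1 lists 9 samples and Dose 3 lists 12: 9 + 12 = 21, and 21 × 2 mL = 42 mL. Both match Appendix 3, so the figure missing from Appendix 6 is unlikely to hide an earlier sample.

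**Tmax under the human description.** The fall between times s and t is 1 − 2^(−(t−s)/t½). For t½ = 503.75 and 565.63 h:
- 0 to 4 h: 0.55% and 0.49%
- 4 to 8 h: 0.55% and 0.49%
- 4 to 24 h: 2.7% and 2.4%

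The assay CV is not in the documents, so 5 to 20% is assumed. I simulated 200,000 profiles on the Dose 1 grid with independent log-normal assay error and t½ = 503.75 h, taking Tmax as the time of the highest value:

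| Assumed CV | 4 h | 8 h | 24 h | 72 h |
|---|---|---|---|---|
| 5% | 42% | 36% | 20% | 2% |
| 10% | 35% | 32% | 24% | 9% |
| 20% | 29% | 28% | 24% | 15% |

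At 565.63 h and 10% CV the split is 34/31/24/10%.

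**Is Table 1 mono-exponential?** If it were, AUCinf would equal Cmax × t½ / ln 2.

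| Single dose | Cmax (µg/mL) | t½ (h) | Implied AUCinf (h·mg/mL) | Stated | Ratio |
|---|---|---|---|---|---|
| 5 mg/kg | 98.22 | 244.74 | 34.7 | 16.10 | 46% |
| 15 mg/kg | 317.57 | 173.15 | 79.3 | 40.26 | 51% |
| 50 mg/kg | 1014.96 | 173.41 | 253.9 | 137.50 | 54% |

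The monkey profiles therefore have a faster early phase. These rows do not say when it happens.

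**How much of it falls before 4 h?** Take C(t) = A·e^(−αt) + B·e^(−βt), with A + B = Cmax and A/α + B/β = AUCinf. β comes from the tabulated half-life, and the early half-life (ln 2/α) is assumed. Example for 15 mg/kg and 24 h: 1/α = 34.62, 1/β = 249.80, and B = (40,260 − 317.57 × 34.62)/(249.80 − 34.62) = 136.0, or 0.428 of Cmax. Then C(4)/Cmax = 0.572 × 0.891 + 0.428 × 0.984 = 0.931, a fall of 6.9%. Across the three doses:

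| Assumed early half-life | Fall by 4 h |
|---|---|
| 0.5 h | 47–54% |
| 2 h | 36–41% |
| 6 h | 18–21% |
| 12 h | 11–12% |
| 24 h | 6.5–7% |
| 48 h | about 4% |
| 72 h | 3–3.5% |

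**Solving for the early half-life.** The weekly 15 mg/kg rows allow this by superposition over four doses, if kinetics are linear. With t½ = 182.81 h, the slow phase carries over 0.5289 + 0.2797 + 0.1479 = 0.9565 of one dose.
- B = (481.76 − 326.27)/0.9565 = 162.6, and A = 326.27 − 162.6 = 163.7.
- The slow phase contributes 162.6 × 263.74 × (1 − 0.5289) ≈ 20,200 h·µg/mL of the first-dose AUC over 168 h (24,500). The fast phase supplies about 4,300.
- So 1/α ≈ 4,300/163.7 ≈ 26.3 h, an early half-life of about 18 h.
- The fall by 4 h is about 8%. It is 6 to 11% for terminal half-lives of 160 to 264 h, and 5 to 22% when the means vary by their standard errors, with 17% of draws unsolvable.

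**AUC.** In the two-phase fits the first 4 h hold 1.4 to 3.1% of AUCinf.

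**The case against.** **The human data look mono-exponential, so little is missed.** This has real force. With an early half-life of 12 to 48 h on Table 1, most of the early phase would still be present at 4 h, and concentration would fall 47 to 59% between 4 and 72 h. The human half-life gives 8 to 9%. A phase that large and slow fits poorly with section 1.5.2. But a phase mostly finished by 4 h would have been invisible to that study. No figure in the documents shows such a phase in humans, and none excludes it.

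**The Tmax and Cmax arguments use different models.** They do, and they should be read as alternatives. If decline is mono-exponential, Cmax loses only about 0.5% and Tmax is noise. If it is two-phase as in the monkey fit, Tmax settles on the earliest samples (about 71% at 4 h and 29% at 8 h, at 10% CV), which is again the grid. Tmax is uninformative either way.

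**A reader might infer from Table 1 that about half the peak is missed.** The documents do not support that. The 46 to 54% ratios measure the whole early phase, in monkeys, and not the part before 4 h. The weekly rows put most of it after 4 h, where the 8, 24 and 72 h samples would catch it.

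**A reader might also infer that the 8 h sample is spare.** That holds only under the mono-exponential model. With early half-lives of 12 to 48 h the 4-to-8 h fall is 4 to 11%.

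**The consequences are limited.** This stands. Cmax is labelled an observed maximum, and the grid delivers one. A similar fractional loss at every dose leaves a power-model slope unchanged, section 8.5 does not name Cmax for dose proportionality, and all analyses are descriptive (section 8.1).

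**Conclusion.** The point holds in a limited form. Recorded Tmax cannot precede about 4 h and carries essentially no information about GMA301. That conclusion needs no monkey data.

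For Cmax, the documents support only that it may understate the peak by an amount they do not fix: about 0.5% if human decline is mono-exponential from time 0, and about 3 to 54% on monkey Table 1 for assumed early half-lives from 72 h down to 0.5 h, with about 8% from the weekly rows. They do not establish a material loss in humans. AUC and clearance are little affected.

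The figures rest on an assumed assay CV of 5 to 20%, assumed early half-lives, linear kinetics for the weekly-row solution, and group means in place of individual profiles. This is a cheap improvement to two secondary endpoints; the primary safety endpoint is untouched.

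**What to change.** - **Appendix 6:** add one PK sample at the end of injection after Dose 1 and after Dose 3. Keep the 8 h sample. State whether post-dose times run from the start or the end of the injection.
- **Appendix 3:** change the PK line to 23 samples and 46 mL (23 × 2). Section 7.1.1 already permits up to 3 extra samples but caps volume at Appendix 3, so that line must move too.
- **Section 2.2.2:** remove Tmax as a secondary endpoint, or state that it is listed and not interpreted. An early sample does not rescue it: with samples added at 0.25 and 1 h, a mono-exponential human profile and 10% CV, Tmax still spreads 22/21/20/19/13% over 0.25, 1, 4, 8 and 24 h.
- **If sampling cannot change:** state that Cmax is the maximum observed from 4 h onward.

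Cost: two extra 2 mL draws per subject and a protocol line. One limit remains. On a flat profile, the maximum of several noisy samples sits above the true peak (about 7% at 10% CV on the present grid, and about 11% with the two early samples simulated above). The end-of-injection concentration should therefore also be listed on its own.
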